| Rationale for Study | FET accumulates in malignant cells within intracranial neoplasms and can be used to detect recurrent disease and characterize grade of glial neoplasms. |
| Primary Objective | To determine if FET PET can differentiate between benign treatment-related changes (TRC) and recurrent glioma in comparison to a composite standard of truth (CSOT) that includes pathology and other clinical information, evaluated using estimates of sensitivity and specificity. |
| Secondary Objectives | 
 1) To determine if FET PET can differentiate between benign TRC and recurrent glioma in comparison to a histopathological standard of truth. 2) To determine if FET PET can differentiate between benign TRC and recurrent glioma in comparison to a CSOT evaluated using estimates other than subject-based sensitivity and specificity. 3) To assess the safety of FET PET, as determined by treatment emergent adverse events (TEAEs) within 48 hours of FET administration. 4) To describe the inter-reader variability between 3 independent blinded readers of FET PET images in their assessments of benign TRC versus recurrent glioma. 5) To describe intra-reader variability between 3 independent blinded readers of FET PET images in their assessments of benign TRC versus recurrent glioma. |

| | |
|------------------------|--|
| Exploratory Objectives | 
 1) To assess relationships between serial FET PET and clinical outcome (benign TRC and recurrence) in patients with recurrent metastatic lesions, recurrent high grade gliomas and recurrent low grade gliomas. 2) To determine if MRI can differentiate between benign treatment-related changes and recurrence. 3) To describe the distribution of the standardized uptake value (SUV) and tumor-to-background ratio (TBR) for observed lesions. 4) To determine if FET PET can differentiate between benign TRC and recurrent metastatic lesions. 5) To determine if FET PET can accurately differentiate between low-grade and high-grade gliomas in population 2. |
| Study Design | This is a prospective, Phase 2, single center, open-label study in patients with intracranial neoplasms. There is a provision of Stopping Rules for the Pediatric patient population. |
| Number of patients | 199 patients, enrolled over four years. 150 patients will be enrolled in patient population 1 and 49 patients will be enrolled in patient population 2. |
| Primary Endpoints | 
 1) Sensitivity of FET PET using a CSOT (subject-level) 2) Specificity of FET PET using a CSOT (subject-level) |
| Duration of Therapy | The study will involve one imaging study involving FET PET for all patients. Adult patients may undergo repeat FET PET. |
| Duration of Follow up | Follow-up will be performed to correlate imaging findings with pathology. |
| Duration of study | The study will reach completion one year after completion of enrollment. |
| Study Drugs | Fluoroethyltyrosine (FET) |
| Safety Assessments | Patient vital signs will be taken immediately before and after the administration of the radiopharmaceutical. The patients will also be asked to report adverse events. |

List of Abbreviations

| | |
|--------|---|
| AE | adverse event |
| CHR | Committee on Human Research (UCSF IRB) |
| CSOT | Composite standard of truth |
| CT | computerized tomography |
| CTCAE | Common Terminology Criteria for Adverse Events |
| DSMC | Data and Safety Monitoring Committee |
| FDA | Food and Drug Administration |
| FDG | Fluorodeoxyglucose |
| FET | Fluoroethyltyrosine |
| FN | False Negative |
| FP | False Positive |
| HDFCCC | Helen Diller Family Comprehensive Cancer Center |
| ICH | International Council for Harmonisation of Technical Requirements for Pharmaceuticals for Human Use |
| IND | investigational new drug application |
| IRB | Institutional Review Board |
| MRI | magnetic resonance imaging |
| NCI | National Cancer Institute |
| NPV | Negative predictive value |
| PET | Positron Emission Tomography |
| PPV | Positive predictive value |
| PRC | Protocol Review and Monitoring Committee (UCSF) |
| RANO | Response Assessment in Neuro-Oncology |
| ROI | Region of interest |
| TBR | Tumor-to-brain ratio |
| TN | True Negative |
| TP | True Positive |
| TRC | Treatment-related changes |

Table of Contents

| | |
|---|----|
| Protocol Signature Page | 2 |
| Abstract | 3 |
| List of Abbreviations..... | 6 |
| Table of Contents..... | 7 |
| 1 Introduction..... | 13 |
| 1.1 Overview..... | 13 |
| 1.2 Background..... | 13 |
| 1.3 Patient Population..... | 14 |
| 2 Objectives of the Study | 14 |
| 2.1 Primary Objective..... | 14 |
| 2.2 Secondary Objectives | 15 |
| 2.3 Exploratory Objectives | 16 |
| 3 Study Design..... | 17 |
| 3.1 Characteristics..... | 17 |
| 3.2 Stopping Rules..... | 17 |
| 3.3 Number of Subjects | 17 |
| 3.4 Eligibility Criteria..... | 17 |
| 3.4.1 Inclusion Criteria | 18 |

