3.3 Number of Subjects

It is anticipated that 199 patients over four years will be enrolled in this study.

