9.1.1 Amended Sample Size Calculation - Protocol Version 2.1

For protocol version 2.1, the sample size was determined based on separate estimates of sample size for each of the co-primary endpoints (sensitivity and specificity). The greater of the two estimates was taken as the required sample size of the study. For each endpoint, the calculation computed the probability of whether the lower limit of a 95% Wilson confidence interval for a binomial proportion was greater than the null proportions of 0.70 and 0.68 for sensitivity and specificity, respectively. Other assumptions include prevalence of glioma recurrence=0.50, observed sensitivity=0.81, and observed specificity=0.79. The sample size for each estimate was set as the smallest positive integer that provides power ≥ 0.80 . Given these assumptions, the estimated sample size is N=118.

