For our sample size analysis, we used a binomial test for proportions. Assuming a misclassification rate of 35% for conventional MRI and 10% for FET PET, 34 patients needed to be imaged with pathologic correlation to demonstrate the difference with a significance level of 0.01 with a power of 90%, and a one-sided test. Our null hypothesis was that there is no difference between MRI and FET PET misclassification rates (H_{null} : MRI_misclass = FET PET misclass = 35%). The alternative hypothesis was that the FET PET misclassification rate is lower (H_{alt} : FET PET misclass < MRI_misclass = 35%). We estimated that 55% of patients would have pathology as a correlate, and we would replace all patients who did not have pathology within four weeks of imaging to fill our primary endpoint. Therefore the total patient population in population 1 with metastatic lesions was 62 patients.

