2. **Recurrent high-grade glioma (Grade 3 and 4):** Based on prior data from UCSF, we anticipated that 70% of patients would have recurrent tumor at the time of imaging (12). Using this same paper as an estimate of misclassification rate using MRI for the characterization of recurrent tumor, resulted in a sensitivity of 82%, specificity of 76%, prevalence of 70% and a misclassification rate of 19.8%. For FET PET, the first paper to publish the sensitivity and specificity of FET PET was Rachinger et al in 2005; they reported a sensitivity, specificity and misclassification rate of 100%, 93% and 2% respectively (45 patients with a prevalence of 69%) (13). A subsequent paper published in 31 patients, 26 of whom had recurrent tumor, had a sensitivity of 100% and a specificity of 84%, resulting in a misclassification rate of 2.6% (14). A third paper looked at the ability to characterize pseudoprogression after radiochemotherapy all of whom had an enhancing lesion on MRI, demonstrated a sensitivity, specificity and misclassification rate of 100%, 91% and 5% respectively (6). No meta-analysis exists for estimating the accuracy of FET PET, and therefore we have selected 5% as a reasonable goal misclassification rate. Our null hypothesis was that there is no difference between MRI and FET PET misclassification rates (19.8% for MRI and 5% for FET PET). For our sample size analysis, we used a binomial test for proportions. Therefore, 27 patients needed to be imaged with pathologic correlation to demonstrate the difference with a significance level of 0.05 with a power of 80%, and using a one-sided t-test. Our null hypothesis was that there is no difference between MRI and FET PET misclassification rates (H_{null} : MRI_misclass = FET PET misclass = 19.8%). The alternative hypothesis was that the FET PET misclassification rate is lower (H_{alt} : FET PET misclass < MRI_misclass = 19.8%). We estimated that 40% of patients would have pathology as a correlate, and we would replace all patients who did not have pathology within four weeks of imaging to fill our primary endpoint. Therefore the total patient population in population 1 with high grade gliomas was 68 patients.

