- 3. Recurrent low-grade glioma (Grade 1 and 2):** We included this population as a secondary endpoint in order to gain information on the role of FET PET in the characterization of low-grade gliomas. We aimed to image 20 patients as part of this cohort to obtain preliminary information about the role of FET PET in this population.

Population 2: For population 2 we selected a misclassification rate for the characterization of tumor as either low or high grade. Most of the data on the literature for the effectiveness of conventional imaging (MRI) for the classification of disease is reported as sensitivity and specificities; the best meta-analysis available suggests that MR spectroscopy has a sensitivity of 75% and a specificity of 70% (15). In this meta-analysis of 25 studies, there were 427 low-grade and 802 high-grade tumors, resulting in a prevalence of 65% for high-grade tumors. Assuming a prevalence of 65%, this would imply a misclassification rate of 27% for conventional imaging. Using a recent FET PET article that demonstrated a sensitivity and specificity of 100% and 73% respectively for the characterization of low-grade and high-grade gliomas with a prevalence of 52%, we estimated a misclassification rate of roughly 13% for FET PET (16). Therefore, our target misclassification rate was 13%. Our null hypothesis was that there is no difference between MRI and FET PET misclassification rates (27% for MRI and 13% for FET PET). For our sample size analysis, we used a binomial test for proportions. Therefore, 49 patients needed to be imaged with pathologic correlation to demonstrate the difference with a significance level of 0.05 with a power of 80%, using a one-sided test. Our null hypothesis is that there is no difference between MRI and FET PET misclassification rates (H_{null} : $\text{MRI_misclass} = \text{FET PET misclass} = 27\%$). The alternative hypothesis is that the FET PET misclassification rate is lower (H_{alt} : $\text{FET PET misclass} < \text{MRI_misclass} = 27\%$).

We estimated that 50 patients with intracranial neoplasms would be enrolled each year, and we estimated that we would enroll 199 patients over the four years of the study.

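### The 150 places in Population 1 were carried over when the primary question became recurrent glioma only, and no current text sets a glioma minimum or a metastasis cap to secure the stated 118.

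*Combined protocol and SAP*

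**What the plan says.** **Current enrolment.** The abstract states that "150 patients will be enrolled in patient population 1 and 49 patients will be enrolled in patient population 2". Section 3.3 repeats the total: "It is anticipated that 199 patients over four years will be enrolled in this study". Sections 1.3 and 3.4.1 still admit three groups to Population 1 (metastases, high-grade glioma, low-grade glioma) and give no number for any of them.

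**Current primary question.** The abstract and section 2.1 confine the primary objective to recurrent glioma versus treatment-related change. Section 9.2.1 builds the efficacy dataset from glioma patients only and drops unreadable scans from it. Section 2.3 lists recurrent metastases as exploratory objective 4.

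**Amended requirement.** Section 9.1.1 asks that the "lower limit of a 95% Wilson confidence interval for a binomial proportion" be "greater than the null proportions of 0.70 and 0.68 for sensitivity and specificity, respectively", with recurrence prevalence 0.50, sensitivity 0.81, specificity 0.79 and power of at least 0.80 for each endpoint. It concludes: "Given these assumptions, the estimated sample size is N=118". It mentions neither the 150 nor the 199.

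**Initial design.** Section 9.1.2, which section 9.1 labels as preceding version 2.1, gives the earlier cohorts: "Therefore the total patient population in population 1 with metastatic lesions was 62 patients"; "Therefore the total patient population in population 1 with high grade gliomas was 68 patients"; and, for low-grade glioma, "We aimed to image 20 patients as part of this cohort". Population 2 was sized at 49.

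**The concern.** The enrolment totals have not moved although the question they serve has. The 62 and the 68 were built to test a misclassification rate against pathology, each inflated for the share of patients expected to have tissue. That endpoint is no longer primary, and metastatic patients no longer enter the efficacy analysis. Yet the total that included them stands, and nothing in the current text says how many of the 150 must be glioma.

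The trial could therefore recruit its 150 Population 1 patients exactly as written and still have fewer than 118 who can answer the primary question. Every metastatic patient beyond a certain number takes a place from the co-primary analysis in favour of an exploratory one. Section 3.5 replaces only participants who do not receive study drug, so an unreadable glioma scan is a further loss.

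**Working it through.** **1. Where the totals come from** (section 9.1.2)

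- Metastatic: 34 / 0.55 = 61.8, rounded up to 62.
- High-grade glioma: 27 / 0.40 = 67.5, rounded up to 68.
- Low-grade glioma: 20.
- Population 1: 62 + 68 + 20 = 150.
- Study: 150 + 49 = 199.

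Both sums equal the current figures in the abstract and section 3.3, so the totals are those of the initial design.

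**2. Gliomas under the only documented mix**

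- 68 + 20 = 88.
- Shortfall against section 9.1.1: 118 − 88 = 30; 88 / 118 = 75%.

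**3. What the 150 can hold**

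- 150 − 118 = 32 metastatic patients at most, so 118 / 150 = 79% of Population 1 must be glioma.
- The superseded mix had 62 / 150 = 41% metastatic.
- The limit of 32 falls by one for each unreadable glioma scan. The documents give no rate for these.
- Keeping 62 metastatic patients as well as 118 gliomas would need 62 + 118 = 180 in Population 1 and 180 + 49 = 229 in all.

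**4. Trying to reproduce the 118**

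Rule from section 9.1.1: for n subjects in a truth class, find the smallest count x whose two-sided 95% Wilson lower limit exceeds the null p0. Power = P(X ≥ x) for X ~ Binomial(n, p1). Total = n / 0.50.

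| Endpoint | p0 | p1 | First n with power ≥ 0.80 | Total at prevalence 0.50 |
|---|---|---|---|---|
| Sensitivity | 0.70 | 0.81 | 120 | 240 |
| Specificity | 0.68 | 0.79 | 126 | 252 |

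The larger total is 252, so 118 is not reproduced. It is close to the per-class count for sensitivity, which would fit an omitted division by prevalence, but that is an inference.

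**5. What the glioma count does to power** (one reader, one endpoint, classes split equally)

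| Gliomas | Per class | Sensitivity: x needed, power | Specificity: x needed, power |
|---|---|---|---|
| 88 | 44 | 37, 38% | 36, 41% |
| 118 | 59 | 49, 42% | 48, 40% |
| 150 | 75 | 61, 54% | 59, 59% |

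Specificity power is marginally lower at 59 than at 44 because the count needed moves in whole subjects. Going from 88 to 118 gains about 4 points on one endpoint and nothing on the other.

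**The case against.** The strongest reply is that the 62/68/20 split is history. It stands only in section 9.1.2, in the past tense, and the reasons for the 62 and the 68 (pathology needed for a misclassification endpoint) have gone. This is correct. A reader might infer from the matching sums that 62 of today's 150 places are reserved for metastases and that the plan is to enrol 88 gliomas. No current passage says so, and 150 places can hold 118 gliomas. A reader might also infer that Population 1 closes on reaching 150. The documents give no closing rule: section 3.3 calls the 199 anticipated, and section 3.8.1 sets primary completion by time. What survives is that nothing in the current text secures 118 either.

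A second reply is that section 9.2.1 counts glioma patients without naming a population, so the 49 in Population 2 might be added: 88 + 49 = 137. That fails on substance. They are imaged before primary treatment, so recurrence versus treatment-related change is not a question about them, and the prevalence in section 9.1.1 is that of glioma recurrence.

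A third reply is that the 30-patient gap hardly matters, since power at 88 and at 118 is nearly the same. This stands as far as it goes. It would be wrong to blame the mix for the loss of 80% power, which comes from the 118 calculation. It does not dispose of the point: power does rise if most or all of the 150 are glioma, and any corrected number will also need a rule on who fills the places.

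**Conclusion.** The point holds as a gap between the amended objective and an inherited enrolment total. The current text sets no glioma minimum and no metastasis cap. The stated 118 is attainable only with at most 32 metastatic patients among the 150, and the one mix on record would deliver 88, which is 75% of the requirement. The 88 is what the superseded split would give, not a planned or observed number.

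The power figures assume prevalence 0.50, true sensitivity 0.81 and specificity 0.79, a strict Wilson criterion, and one reader and one endpoint at a time. The success rule in section 9.2.2, which requires both endpoints to be met by the same two of three readers, was not modelled.

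This is more than a missing detail, because settling it either changes who is enrolled or corrects a figure on which the primary analysis relies. It is not, taken alone, the reason the trial would fall short of 80% power.

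**What to change.** Within the existing 150 places, state in the abstract and section 3.3 a minimum number of evaluable Population 1 glioma patients: 118, or its corrected value once section 9.1.1 has been rechecked. Limit metastatic patients to the places that remain after an allowance for unreadable scans, and say that Population 2 does not count towards the minimum. If the corrected value exceeds 150, as the recalculation above suggests, the sponsor must either enlarge Population 1 or state openly the power that 150 can give.

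If accrual is too advanced to change the mix, restate in section 9.1.1 the number of Population 1 gliomas actually expected and the power that number gives, in place of the bare 118.

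The cost is an amendment and a running glioma count in the screening log. Holding to 118 needs no extra patients. The price is fewer metastatic patients for exploratory objective 4 and possibly slower accrual. The amendment should not claim that the change restores the stated power.

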1.1 Overview

Imaging using the amino acid-based PET tracer O-(2-[¹⁸F]fluoroethyl)-L-tyrosine (FET) is a promising imaging platform for both primary and secondary brain neoplasms. However, widespread incorporation of FET PET into the routine clinical management of brain tumor patients has not occurred within the United States. The primary issue associated with this promising imaging agent is the lack of approval by the Food and Drug Administration (FDA). The goal of this protocol is to obtain prospective data and the safety and efficacy of FET for the detection of intracranial neoplasms with the goal to submit a New Drug Application (NDA) for this agent. To date we are not aware of an institution on the United States who has previously obtained an IND for FDA or submitted an FDA application. We are aiming to achieve two indications with this study. The first is the ability to accurately detect recurrent disease in patients who have previously undergone surgery and/or radiation. The second indication is the ability to distinguish low-grade glial neoplasms from high-grade glial neoplasms.

1.2 Background

Glial tumors are the most common primary neoplasms affecting the central nervous system. This heterogeneous group of tumors is classified as low or high grade based on histologic features such as the presence of increased cellularity, mitotic activity or necrosis (1). Due to their infiltrative nature, gliomas are rarely cured via surgical resection, contributing to a disproportionately high morbidity and mortality (2,3).

Imaging techniques play an important role in the clinical management of neuro-oncology patients. Anatomic imaging with magnetic resonance imaging (MRI) is the mainstay for initial diagnosis, treatment planning and post-treatment follow-up of brain tumors given its widespread availability, high spatial resolution and excellent soft tissue contrast. However, conventional MRI techniques have several important limitations in brain tumor imaging, including those currently used to define disease progression as part of the RANO criteria (Response Assessment in Neuro-Oncology) (4). Contrast enhancement, a marker of blood-brain barrier permeation, is neither sensitive nor specific for the presence of tumor tissue. The majority of low-grade glial neoplasms do not enhance, while inflammatory processes common in the postsurgical/post treatment setting often enhance avidly. A diagnostic dilemma occurs in up to 30% of patients within the first 12 weeks following completion of chemoradiotherapy, whereby an enlarging area of contrast enhancement on MRI may represent either early tumor progression, which necessitates a change in the ongoing treatment regimen, versus “pseudoprogression”, which represents non-progressive treatment-related change (TRC) that does not require alteration of the treatment regimen.

Positron-emission tomography (PET), which has the capability to image specific metabolic processes using radiolabeled endogenous molecules, is another imaging modality with high potential for use in neuro-oncology. The most widely used PET tracer is the glucose analogue fluorodeoxyglucose (FDG). However, FDG is not ideal for brain tumor imaging given the high background uptake of normal brain parenchyma and limited specificity in distinguishing between progressive tumor and post-treatment inflammation. O-(2-[¹⁸F]fluoroethyl)-L-tyrosine (FET) is an amino acid-based PET tracer with high uptake in brain tumors and relatively low uptake in normal brain parenchyma (5). Various studies have demonstrated the ability of FET PET to detect recurrent gliomas with higher sensitivity and specificity compared with conventional imaging techniques (6,7). Additionally, the value of using FET PET tumor grading has also been shown (8).

We believe that FET PET has significant promise in the imaging and characterization of patients with primary and secondary intra-cranial neoplasms. This protocol is intended to focus on the two main applications of the radiotracer in order to obtain the data required for the submission of an NDA application from the FDA.

Of note, we will follow-up patients without histologic correlation in order to determine the accuracy of imaging follow-up as a possible replacement for histology as a marker of disease recurrence. This will be the motivation and goal of the study's primary objective.

